6.2 Secondary objective

To determine whether CGM systems accurately record hypoglycaemia and can be used in this context

6.3 Primary endpoint

Arm 1 -

Outpatient - CGM findings reflect patient's fingerprick glucose readings

- Episodes of true hypoglycaemia (as decided by finger prick glucose testing) are captured by the CGM device

- CGM detects hypoglycaemia whilst patient is asleep

Inpatient - 72 hour fast - CGM device calls hypoglycaemia when fingerprick/lab glucoses also do

Arm 2 -

Blinded phase - CGM findings reflect patient's fingerprick glucose readings - any episodes of true hypoglycaemia (as decided by fingerprick glucose testing) are captured by CGM device

unblinded phase - CGM recordings help with titration of anti hypoglycaemic medications and this reduces overall incidence of hypoglycaemic episodes or duration of time spent in hypoglycaemic range

For patients experiencing asymptomatic hypoglycaemic episodes, a reduction in asymptomatic hypoglycaemic episodes and regaining of hypoglycaemic symptoms.

For patients with symptomatic hypoglycaemia, a reduction in symptomatic episodes.

7. Study population

Clinicians in the endocrinology department at St Bartholomew's hospital will be notified of this study and encouraged to refer forward suitable patients from their clinics.

Arm 1

Patients referred to the endocrinology department at St Bartholomew's hospital for investigation of suspected hypoglycaemia by either GPs or other clinical teams in the same or external NHS trusts will be referred onwards to the study team by the doctor that sees them for their routine clinical care.

Arm 2

Patients known to the endocrinology department at St Bartholomew's hospital with hypoglycaemia that are medically managed or who are to start medical management will be referred to the study team by the doctor that sees them for their routine clinical care.

Some patients who are found to have hypoglycaemia through arm 1 of this study will be automatically offered the chance to partake in arm 2 if they are to have medical treatment.

No vulnerable groups will be included – all patient will be able to give valid consent on their own behalf
All patients will be able to understand sufficient English to give informed consent on their own behalf.

Inclusion Criteria

Able and willing to give informed consent. No vulnerable adults will be included.
Either conventional gender, or non-binary.
Age >18 years
Any ethnicity
Any socio economic group
Medical condition as detailed above – arm 1 under investigation for possible/probable hypoglycaemia
Arm 2 – on medical therapy for established hypoglycaemia

Exclusion criteria

Unwilling or unable to give consent
Unable to speak sufficient English to give consent and understand study requirements
Age<18
Lack of capacity to consent
Underlying hepatic condition
Current excessive alcohol consumption (men regularly consuming >50 units/week, women >35 units/week)
Diabetes Mellitus
Current use of Diabetic medication or insulin
Currently pregnant
Any patient on haemo or peritoneal dialysis

Length of study participation

Arm 1 - investigation of hypoglycaemia - maximum of 10 days of monitoring (5 days as an outpatient, max 5 days as an inpatient).
Arm 2 - evaluating anti hypoglycaemic drugs - maximum of 10 days of initial monitoring (investigator and patient blinded to CGM results), then up to a maximum of a further 20 days (unblinded) monitoring, likely to be far less than this though.

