6.1 Primary objective

- 1) Use CGM (blinded to the patient and investigator) in advance of standard investigations (where possible) in order to record whether patient symptoms correlate with recorded hypoglycaemia. This may exclude hypoglycaemia as a cause of symptoms and allow the patient to avoid a prolonged inpatient investigation.
- 2) Use CGM technology (blinded to the patient and investigator) alongside standard investigations for patients with both reactive and spontaneous hypoglycaemia to evaluate the relative efficacy of the two methods in detecting hypoglycaemia episodes.
- 3) Use CGM (blinded to the patient and investigator) to record frequency of hypoglycaemia after medical treatment has been initiated in order to assess its

effectiveness in detecting hypoglycaemic episodes of which the patient may not have been aware, potentially reducing the need for painful fingerprick glucose testing.

4) Use CGM (unblinded) to titrate medication to abolish hypoglycaemia in order to improve outpatient management and improve patient safety. The Dexcom system has an alarm to alert patients to hypoglycaemia which will be used in the unblinded phase.

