12.2 Method of analysis

P<0.05 will be considered statistically significant

Arm 1

Positive and negative predictive value of CGM diagnosis of hypoglycaemia as an outpatient or an inpatient vs 72 hour fast (considered the 'gold standard')

Arm 2

In each patient, comparison of number of episodes of hypoglycaemia by finger prick glucose vs CGM vs symptoms during CGM blinded phase.

Severity of hypoglycaemia excursions

Amount of time spent in the hypoglycaemic range after medication titration – as measured by area under the curve on a time vs glucose graph generated by CGM machine. Comparisons of mean hypoglycaemic frequency and time within hypoglycaemic range within patients (blinded vs unblinded phase) using paired T test.

Change in hypoglycaemia questionnaire score before/after CGMs monitoring and medication titration

Regain of symptomatic hypoglycaemia in patients with asymptomatic hypoglycaemia, reduction of symptomatic hypoglycaemia in other patients.

13. Ethics

- Informed consent

Patients will be offered the chance to partake in the study should their treating consultant feel that they meet the inclusion criteria. Declining an invitation to take part in the study or leaving at any time means that the patient will default back to standard of care investigations. Their care will not be prejudiced or compromised in any way through either taking part or not taking part in the study.

- Recruitment

Only patients under investigation/treatment for hypoglycaemia at St Bartholomew's hospital will be considered for entry to the study. Patient being treated/investigated elsewhere who wish to be considered for the study would need to have their care transferred to St Bartholomew's by their GP/current endocrinologist.

- Inclusion / exclusion criteria

Inclusion/exclusion criteria is intended to screen out patients who have conditions that may affect their blood glucose (Diabetes Mellitus, underlying hepatic pathology) or in whom CGM is not recommended (pregnancy, critical illness) or in whom hypoglycaemia may be caused by extrinsic factors such as Diabetes medication.

- Study design

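### The hypoglycaemia-detection items in section 6.3 measure sensitivity only, or have no reference at all, so a CGM sensor that over-calls lows satisfies each of them; other parts of the protocol cover false calls only in part

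*Protocol*

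**What the plan says.** Section 6.3 lists these detection items:

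- Arm 1 outpatient, general: "Outpatient - CGM findings reflect patient's fingerprick glucose readings".
- Arm 1 outpatient, capture: "Episodes of true hypoglycaemia (as decided by finger prick glucose testing) are captured by the CGM device".
- Arm 1 outpatient, sleep: "CGM detects hypoglycaemia whilst patient is asleep".
- Arm 1 inpatient: "CGM device calls hypoglycaemia when fingerprick/lab glucoses also do".
- Arm 2 blinded: the general agreement phrase, then a dash, then "any episodes of true hypoglycaemia (as decided by fingerprick glucose testing) are captured by CGM device".

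The secondary objective (6.2) is "To determine whether CGM systems accurately record hypoglycaemia and can be used in this context". The first primary objective (6.1) adds a rule-out purpose: "This may exclude hypoglycaemia as a cause of symptoms and allow the patient to avoid a prolonged inpatient investigation".

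Section 12.2 plans positive and negative predictive value (PPV, NPV) of the CGM diagnosis against the 72 hour fast in arm 1. For the arm 2 blinded phase it plans a "comparison of number of episodes of hypoglycaemia by finger prick glucose vs CGM vs symptoms during CGM blinded phase". Section 8 also plans to match CGM data with diary and laboratory values to check concordance. In the unblinded phase only, it asks patients to confirm low CGM readings by finger prick.

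**The concern.** Whether a device records hypoglycaemia accurately has two parts: does it call low when glucose is low, and does it stay silent when glucose is not low? The capture items in 6.3 ask only the first. On them a sensor can only gain by reading lower.

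Three uses of the results depend on the second part. The accuracy conclusion in 6.2 cannot rest on capture alone. The rule-out aim in 6.1 needs CGM to be silent in people without hypoglycaemia, since otherwise few could be spared admission. Objective 3 in 6.1 looks for episodes of which the patient was unaware, and in the arm 2 blinded phase a false CGM low looks the same as such an episode. The blinded-phase CGM data are then reviewed, with the diary, when medication is adjusted (section 8), so the frequency of false lows is of practical interest.

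**Working it through.** The protocol gives no figure to reproduce here: 30 patients are planned as a pilot (12.1), with no target for capture or false calls. The check is therefore on what each item counts.

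**Step 1: the paired table.** For each CGM value paired with a finger-prick or laboratory reference:

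| | Reference low | Reference not low |
|---|---|---|
| CGM low | a | b |
| CGM not low | c | d |

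- Capture items (arm 1 outpatient, arm 1 inpatient, arm 2 blinded): a/(a + c). Cells b and d do not enter.
- Sleep item: met by any CGM low during sleep, true or false.
- Missing measure, the false-call rate: b/(b + d).

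**Step 2: what capture hides.** Let Se be sensitivity, Sp specificity and p the share of references that are low. The documents do not give p, so 0.05 to 0.50 is assumed. The Se and Sp values are also assumed, to show the logic; they are not estimates for this device.

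- Capture = Se
- False-call rate = 1 − Sp
- PPV = Se·p / [Se·p + (1 − Sp)(1 − p)]
- Agreement = Se·p + Sp(1 − p)

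| Sensor | Capture | False-call rate | PPV, p = 0.05 | p = 0.10 | p = 0.20 | p = 0.30 | p = 0.50 |
|---|---|---|---|---|---|---|---|
| Always low (Se 1, Sp 0) | 100% | 100% | 5.0% | 10.0% | 20.0% | 30.0% | 50.0% |
| Over-calling (Se 1, Sp 0.60) | 100% | 40% | 11.6% | 21.7% | 38.5% | 51.7% | 71.4% |
| Balanced (Se 0.95, Sp 0.95) | 95% | 5% | 50.0% | 67.9% | 82.6% | 89.1% | 95.0% |

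For example, the over-calling sensor at p = 0.10 has PPV = 0.10 / (0.10 + 0.40 × 0.90) = 0.10/0.46 = 21.7%.

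Capture ranks the balanced sensor last; PPV and the false-call rate rank it first. For the always-low sensor, agreement equals p and NPV is undefined. NPV does not expose the over-calling sensor, because with Se = 1 it is 100% at every p.

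**Step 3: which references exist (section 8).**

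| Setting | Reference readings | Agreement line in 6.3? | Analysis in 12.2 |
|---|---|---|---|
| Arm 1 outpatient | Finger prick at symptoms | Yes, without a metric | PPV/NPV against the fast |
| Arm 1 inpatient | Twice-daily venous glucose, routine finger pricks, extra tests at symptoms | No | PPV/NPV against the fast |
| Arm 2 blinded | Finger prick at symptoms | Yes, without a metric; may be read as capture only | Episode counts |

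The inpatient setting has the best non-low references: a full 72 hour fast gives 3 days × 2 = 6 scheduled venous values, plus routine finger pricks. Yet its item in 6.3 is the one with no agreement criterion.

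**Step 4: the arm 2 count comparison.** Finger-prick episodes number a + c, now counting episodes. CGM episodes number a + U + F, where U are true lows with no finger prick and F are false lows. The difference is U + F − c. Counts alone cannot separate U from F, and a symptomless CGM low in the blinded phase has no planned finger prick to settle it.

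**The case against.** A reader might infer that false CGM lows are never penalised anywhere in the plan. The documents do not support that:

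- The arm 1 outpatient agreement line is a separate criterion, not limited to lows. Symptoms can occur at normal glucose, which objective 1 sets out to examine, and an always-low sensor would not agree with those readings.
- PPV in 12.2 falls with false positives in arm 1, and a comparison with the fast suits the rule-out aim.
- The section 8 concordance check is not restricted to low values.
- Low CGM readings are to be confirmed by finger prick in the unblinded phase, and the first titration review uses the diary as well as CGM. It would be too strong to say that false lows pass unchecked into titration.

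All of this stands, but as partial cover. The agreement line and the concordance check have no metric. That could be left to an analysis plan, but the direction of the capture items is fixed in 6.3. In arm 2 the dash can be read as defining agreement by capture alone, although that is one of two readings. PPV is set against the fast, so apparently per patient (the text does not say), and 6.3 does not name it. Confirmation by finger prick does not reach the blinded phase.

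A reader might also infer that a biased sensor would pass the trial, and try to put a size on this by simulation. The protocol sets no pass mark, so there is nothing to pass. The device figures in section 5 also count against a strongly biased sensor. Below 3 mmol/L, 85% of readings within 20% and 93.5% within 30% imply an unbiased normal error SD of 20/1.44 = 13.9% to 30/1.84 = 16.3%. With such an SD, a sensor reading 20% low would be within 20% only about half the time, not 85%. Such a simulation illustrates direction; it is not a magnitude for this device.

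**Conclusion.** The point holds in a limited form. The three capture items in 6.3 are sensitivities and the sleep item has no reference, so over-calling satisfies each of them; this follows from the wording and needs no numerical assumption. The arm 1 inpatient item is the clearest case, since scheduled non-low references exist and go unused there. The arm 2 blinded phase is the least protected, because its only analysis is a count comparison in which false lows and unaware hypoglycaemia look alike.

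Over the assumed p of 0.05 to 0.50, an always-low sensor would show 100% capture with a PPV of only 5% to 50%. No size can be given for the actual device, because the documents report no false-call rate. Arm 1 PPV, the agreement line and the concordance check reduce the problem but are not tied to the capture items. For a 30-patient pilot this should be corrected before analysis; it does not invalidate the study.

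**What to change.** In 6.3 and 12.2:

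1. Beside the proportion of low finger-prick or laboratory readings that CGM also calls low, report the proportion of non-low readings at which CGM calls low. Give both with patient-clustered confidence intervals, because readings repeat within patients.
2. Use the scheduled inpatient venous and finger-prick readings as the main source of non-low references. Report symptom-triggered readings with normal glucose separately for arm 1 outpatients and the arm 2 blinded phase.
3. Link the arm 1 PPV/NPV analysis in 12.2 explicitly to 6.3, and state its unit of analysis.
4. State that the accuracy conclusion in 6.2 needs both the capture and the false-call result.
5. State that an excess of CGM over finger-prick episodes in the arm 2 blinded phase is not by itself evidence of unaware hypoglycaemia.

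The cost is wording in two sections and one extra clustered tabulation of data already collected, with no new samples or visits. The headline may look less favourable to CGM.

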	
hypoglycaemia in order to improve outpatient management and improve patient safety. The Dexcom system has an alarm to alert patients to hypoglycaemia which will be used in the unblinded phase.
 
Aims
 
There will be two main arms to the study;
 
 1) Investigation of patients suspected of having hypoglycaemia (spontaneous or reactive) alongside standard investigations 2) Management of patients with confirmed hypoglycaemia who are medically managed to see if continuous glucose monitoring can play a role in abolishing asymptomatic hypoglycaemia through optimisation of medicines.
Number of participants	30
Inclusion and exclusion criteria	
Inclusion Criteria
 
Able and willing to give informed consent. No vulnerable adults will be included.
 
Either conventional gender, or non-binary.
 
Age >18 years
 
Any ethnicity
 
Any socio economic group
 
Medical condition as detailed above – arm 1 under investigation for possible/probable hypoglycaemia
 
Arm 2 – on medical therapy for established hypoglycaemia
 
Exclusion criteria
 
Unwilling or unable to give consent
 
Unable to speak sufficient English to give consent and understand study requirements
 
Age<18 or >90 years
 
Lack of capacity to consent
 
Underlying hepatic condition
 
Current excessive alcohol consumption (men regularly consuming >50 units/week, women >35 units/week)
 
Diabetes Mellitus
 
Current use of Diabetic medication or insulin
 
Currently pregnant
 
Any patient on haemo or peritoneal dialysis

Statistical methodology and analysis (if applicable)	
Study duration	1 year

5. Introduction

Suspected reactive and spontaneous hypoglycaemia can be a challenging problem to investigate. Definitive diagnosis currently relies upon the patient experiencing symptoms, reporting them accurately and then a series of complex investigations.

Current standard of care tests

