Patients who have been diagnosed with spontaneous hypoglycaemia which requires medical therapy will be given a CGM kit and a finger prick glucose monitoring device and glucose monitoring diary. Patients will take the standard medical therapy and perform finger prick glucose testing when they experience symptoms that they attribute to hypoglycaemia. These values will be recorded in the glucose monitoring diary. After (up to) 10 days of blinded CGM monitoring, the diary and CGM data will be reviewed. A member of the endocrine team (consultant or registrar with consultant approval) will then make changes to the medical therapy in order to abolish any remaining episodes of hypoglycaemia. Patients will then wear the CGM device in unblinded mode for up to a further 20 days (though likely to be far less) in order to facilitate further medication titrations. Patients will be asked to confirm low CGM glucose readings during this time with a finger prick glucose measurement.

The study organisers will observe the glucose data obtained from the CGM and match it with finger prick glucose readings (from glucose monitoring diaries) and lab glucose data to check for concordance.

CGM data (in conjunction with glucose monitoring diaries) will be scrutinised and compared against drug regimens to see which doses needed to be altered, or where additional medication is required.

Patients will complete a modified Clarke and Gold hypoglycaemia questionnaire at the start of arm 2. They will complete an adapted questionnaire prior to surgery for their hypoglycaemia (if indicated) or at 6 months after the start of arm 2 – whichever comes first.

9. Study procedures

Arm 1

Patients will be recruited either through attendance at endocrinology outpatients at St Bartholomew's hospital or through inpatient transfer to St Bartholomew's hospital – both with suspected diagnoses of hypoglycaemia.

If attending the outpatients department with suspected hypoglycaemia and thought to be suitable for the study, then the patient will meet a member of the study team after their outpatient appointment or they will be offered an appointment to discuss the study at a mutually convenient time. Informed consent will be obtained during this meeting.

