A further appointment will then be made to discuss the results of the initial CGM and to titrate the drug regimen. This appointment could be face to face or by telephone.

If periods of hypoglycaemia persist then alterations to the drug regime will be made and the patient will continue to wear the CGM device, but both they and the investigators will be unblinded to the CGMs allowing further titrations to the anti-hypoglycaemia medications to be made by telephone. Patients will be asked to take a finger prick glucose reading to confirm any low CGM readings.

At the conclusion of the patient's study participation, they will be asked to return the CGM receiver.

At 6 months, or prior to surgery to cure the hypoglycaemia (whichever comes first) the patient will attend the hospital to complete an adapted version of the modified Clarke and Gold hypoglycaemia questionnaire.

Schedule of study interventions

Study intervention	Visit 1	Visit 2	Visit 3	Visit 4	Visit 5
Meet with study team to learn about study and give Informed consent	x				
Placement of CGM device, receive finger prick glucose meter and diary Complete hypoglycaemia questionnaire	Either x	Or x			
Review of CGM data and titration of medication and unblinding of CGM device		Either x	Or x		
Subsequent medication titration by telephone			Either x	Or x	
Return CGM receiver device				x	
Complete adapted hypoglycaemia questionnaire					x

Study Drugs/device

The drugs used to treat hypoglycaemia will be those that are current standard of care and the doses/indications will not vary from standard practice.

We will use a Dexcom G6 continuous glucose monitoring device to record patient's blood glucose to aid diagnosis of hypoglycaemia prior to and during standard of care hospital investigations. The device's software will be modified by Dexcom to disable hypoglycaemia alarm functions, visible blood glucose readout (on the receiver device) and the ability to view blood glucose remotely.

For the unblinded component of arm 2 these functions will be restored

Concomitant medications

Patients will continue to take all other prescribed medications.

Criteria for discontinuation

Patients that become pregnant, or develop a critical illness during the study will be withdrawn as Dexcom devices are unreliable in these circumstances.

Procedure for data collection

Arm 1 – CGM data from each Dexcom device will be downloaded at the end of the inpatient investigations.

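### The arm 2 primary endpoint credits CGM with helping titration, but the protocol provides for no titration decision made without CGM, so CGM's own contribution cannot be separated out

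*Protocol*

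**What the plan says.** The protocol's second main aim (section 4) is "to see if continuous glucose monitoring can play a role in abolishing asymptomatic hypoglycaemia through optimisation of medicines". Section 6.3 turns this into a primary endpoint for the unblinded phase of arm 2: "CGM recordings help with titration of anti hypoglycaemic medications", with the consequence that hypoglycaemia occurs less often or lasts less long. That sentence has two halves: CGM helps the titration, and hypoglycaemia falls because of it.

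Section 8 describes the step at which treatment is first adjusted: "After (up to) 10 days of blinded CGM monitoring, the diary and CGM data will be reviewed". The endocrine team "will then make changes to the medical therapy in order to abolish any remaining episodes of hypoglycaemia". Section 9 places this in a single contact: "A further appointment will then be made to discuss the results of the initial CGM and to titrate the drug regimen". Section 8 adds that "CGM data (in conjunction with glucose monitoring diaries) will be scrutinised and compared against drug regimens to see which doses needed to be altered". Further titration by telephone follows while CGM is visible to patient and team.

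Section 12.2 plans two analyses that bear on this. In the blinded phase, each patient's episode counts by finger prick, CGM and symptoms are compared. Across phases, mean hypoglycaemia frequency and time in the hypoglycaemic range are compared within patients by a paired t test, blinded against unblinded. Section 17.1 says that the alarms and glucose display are off in the blinded phase and on in the unblinded phase.

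**The concern.** To say that CGM helped a titration is to say that the decision would have been different, or would not have been made, without it. That needs some record of the decision that diary, finger pricks and symptoms would have led to. The visit schedule and data collection (section 9), the analysis (section 12.2) and the source data (section 15.2) provide for no such record, and no group or period is titrated without CGM.

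A fall in hypoglycaemia after titration looks the same whether CGM prompted the change or the diary would have prompted the identical change. The trial could then report its second aim as met when it had shown only that patients whose treatment was adjusted did better.

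**Working it through.** There is no figure in the plan to reproduce. The sample size of 30 (section 12.1) is a pilot number with no effect size, standard deviation or power behind it, and no number is given for arm 2. The first two steps set the provisions against the endpoint; the other two are illustrations on assumed inputs.

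**1. What addresses each half of the endpoint.**

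- *CGM helps titration.* The blinded-phase comparison of finger prick, CGM and symptom counts shows what CGM detected that the other sources missed. This is detection. It bears on titration only indirectly, because an extra episode on CGM need not change a prescription. Setting CGM and diaries against drug regimens uses both sources jointly.
- *Hypoglycaemia falls.* The paired t test addresses this directly.

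**2. What differs between the two phases being tested.** The regimen is changed, CGM data inform that change and later ones, and the alarms and display are switched on. All three move together, so the difference belongs to the package.

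**3. How readily the test would be significant if CGM altered no decision.** Assume that titration alone, which the diary would have prompted anyway, produces a standardised paired change d (mean change divided by the standard deviation of the changes). Take a two-sided 5% level; section 12.2 states P<0.05 without sidedness. With n patients, the t statistic is noncentral t with n − 1 degrees of freedom and noncentrality d√n, so

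P(significant) = 1 − F(t₀.₉₇₅; n − 1, d√n) + F(−t₀.₉₇₅; n − 1, d√n).

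For n = 15 and d = 0.8, the noncentrality is 0.8 × √15 = 3.10 and the probability is 0.82. Over a range of assumed values:

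| Arm 2 patients (assumed) | d = 0.5 | d = 0.8 |
|---|---|---|
| 10 | 0.29 | 0.62 |
| 15 | 0.44 | 0.82 |
| 20 | 0.57 | 0.92 |
| 30 | 0.75 | 0.99 |

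A significant phase difference is therefore not evidence that CGM changed the titration.

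**4. What a two-step record would give.** If x of n first decisions change once CGM is opened, the exact (Clopper-Pearson) 95% limits are the 0.025 quantile of Beta(x, n − x + 1) and the 0.975 quantile of Beta(x + 1, n − x).

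- 8 of 15 (53%): 27% to 79%
- 0 of 15: upper limit 1 − 0.025^(1/15) = 22%
- 5 of 10 (50%): 19% to 81%
- 12 of 30 (40%): 23% to 59%

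The counts and denominators are assumed. The intervals are wide at any size this trial can reach.

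**The case against.** The other side has several fair points.

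- **It is a feasibility pilot.** Objective 4 (section 6.1) is to use unblinded CGM to titrate and claims no advantage over diary-led titration. That is so, but section 6.3 still lists help with titration, and a fall resulting from it, as a primary endpoint. Making that wording descriptive would remove the attribution, but the question in the second aim would stay unanswered.
- **There is some evidence already.** A reader might infer that the endpoint has no comparator, or that its first half is wholly unobserved. The documents do not support either. The reduction half has a within-patient comparison, though a confounded one, and the blinded-phase counts give indirect evidence on the first half.
- **The diary may be nearly empty.** Blinded-phase finger pricks are prompted by symptoms (section 8), so for patients with only asymptomatic episodes a diary that would have led to the same change is an unlikely extreme. This stands. The ambiguity is greatest for symptomatic patients, and the two groups should be reported apart if numbers allow.
- **The text gives no order of opening, and the case report form is not shown.** This also stands. One cannot say that diary and CGM are opened at the same moment, or that nobody writes down a prior view. One can say that the protocol does not provide for it.
- **It might be recovered later.** An independent clinician could judge the diaries and regimens without CGM. That would be useful, but it would not be the treating clinician's own decision, which has to be recorded before CGM is seen.
- **The remedy is partial.** It reaches the first titration only. Later telephone titrations take place with CGM visible and with finger pricks taken to confirm low CGM readings, so the diary is no longer independent of CGM. A clinician who knows that CGM comes next may also defer, which would inflate the proportion changed. Both limits stand and should be stated.

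**Conclusion.** The concern holds for the attribution to CGM. Followed as written, the protocol can show whether hypoglycaemia falls between the phases and what CGM detected that finger pricks and symptoms did not. It cannot show that CGM altered a titration, and the phase comparison cannot separate CGM from diary-prompted titration or from the alarms and display.

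A reader might go further and infer that CGM adds nothing, or that any fall would be wrongly credited to it. The documents support neither; they leave CGM's share unknown. The probability of 0.82 shows that significance alone would not settle the matter. It rests on an assumed 15 patients and an assumed change of 0.8, and ranges from 0.29 to 0.99 over the values tabulated.

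The point is a worthwhile improvement to one part of one primary endpoint and does not undermine the rest of the study. A later analysis plan could describe the phase change correctly, but it could not recover the treating clinician's pre-CGM decision.

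**What to change.** At the existing review that ends the blinded phase of arm 2:

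1. Before the CGM download is opened, the reviewing clinician records on the case report form the provisional decision from diary, finger pricks and symptoms alone: change or no change, and which.
2. The CGM data are then opened and the final decision is recorded. Care follows the final decision only.
3. Report the proportion of patients whose first titration decision changed after CGM was seen, with an exact 95% confidence interval, separately for symptomatic and asymptomatic hypoglycaemia if numbers allow.
4. State that this measures the first titration only, excludes later telephone titrations under visible CGM, and does not show that the changed decisions caused any fall.
5. In sections 6.3 and 12.2, describe the blinded-to-unblinded change as the effect of the whole package (titration, CGM data, alarms and display).

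The cost is one form page and a few minutes per arm 2 patient at a contact already planned. There is no extra visit or test and no change to treatment. The drawbacks are wide intervals and possible bias in a provisional decision made in the knowledge that CGM follows.

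### The Arm 2 unblinded primary endpoint can be met on incidence or on duration, each with its own paired t test at P<0.05, among about eight primary items with no hierarchy

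*Protocol*

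**What the plan says.** Section 6.1 of the protocol labels all four objectives primary. Section 6.3, headed in the singular, then lists about eight primary items:

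- Arm 1, outpatient: agreement of CGM with finger-prick readings; capture of true episodes; and "CGM detects hypoglycaemia whilst patient is asleep".
- Arm 1, inpatient: "CGM device calls hypoglycaemia when fingerprick/lab glucoses also do".
- Arm 2, blinded phase: agreement with finger-prick readings and capture of true episodes.
- Arm 2, unblinded phase: CGM helps with titration and "this reduces overall incidence of hypoglycaemic episodes or duration of time spent in hypoglycaemic range".
- Arm 2, patients with asymptomatic episodes: "a reduction in asymptomatic hypoglycaemic episodes and regaining of hypoglycaemic symptoms".
- Arm 2, the remaining patients: "For patients with symptomatic hypoglycaemia, a reduction in symptomatic episodes".

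No item is named as the one that decides.

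Section 12.2 opens with one general rule, "P<0.05 will be considered statistically significant". For Arm 1 it gives "Positive and negative predictive value of CGM diagnosis of hypoglycaemia as an outpatient or an inpatient vs 72 hour fast", which is estimation. For Arm 2 it lists several summaries but names a hypothesis test only once: "Comparisons of mean hypoglycaemic frequency and time within hypoglycaemic range within patients (blinded vs unblinded phase) using paired T test". Those two quantities are the two halves of the unblinded endpoint.

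**The concern.** Section 6.3 joins two outcomes with an 'or', and section 12.2 gives each its own test at the full threshold. A claim that CGM-guided titration reduces hypoglycaemia can therefore rest on whichever test comes out below 0.05, so the stated level does not describe the claim as a whole.

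The 'or' is also silent on direction. Fewer but longer episodes, with more total time low, would satisfy it, as would shorter but more frequent ones. The design could plausibly separate the two measures. In the unblinded phase the hypoglycaemia alarm is active (sections 6.1 and 17.1) and patients confirm low CGM readings by finger prick (sections 8 and 9), so alerted patients might shorten episodes without having fewer of them.

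The wider list has a related weakness. With about eight primary items and no order among them, nothing in the protocol says which result answers the study question for either arm.

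**Working it through.** The protocol gives no error rate, power, effect size or SD, so there is no figure of its own to reproduce.

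**Inputs**

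- Threshold: 0.05 (section 12.2). Sidedness is not stated; two-sided is assumed, which is 0.025 in the favourable direction.
- Tests for the unblinded endpoint: two paired t tests (section 12.2), joined by 'or' (section 6.3).
- Sample size: 30 in total (section 12.1). The split between arms is not given, so 10 to 30 Arm 2 patients are assumed.
- Correlation between the two within-patient changes: not given; 0 to 0.9 assumed.

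**Count of primary items**

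Arm 1 has 4. Arm 2 has 4 if each compound item counts once, giving 4 + 4 = 8. If the Arm 2 blinded, unblinded and asymptomatic items are each split in two, Arm 2 has 2 + 2 + 2 + 1 = 7, giving 4 + 7 = 11.

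**Error of the 'or' rule with no true effect, independent measures**

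- At least one P<0.05 in either direction: 1 − (1 − 0.05)² = 1 − 0.9025 = 9.75%.
- At least one false reduction: 1 − (1 − 0.025)² = 1 − 0.9506 = 4.9%, against 2.5% for one measure.

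These two figures do not depend on the number of patients, provided each t test holds its nominal level.

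**Correlated measures**

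Simulation, 100,000 replicates per setting, normally distributed differences, range over n = 10, 15, 20 and 30:

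| Correlation | Either test P<0.05 | Either a false reduction | One significantly reduced, other in the wrong direction |
|---|---|---|---|
| 0 | 9.6% to 9.9% | 4.8% to 5.1% | 2.4% to 2.6% |
| 0.5 | 9.1% to 9.3% | 4.6% | 0.5% to 0.6% |
| 0.7 | 8.4% to 8.5% | 4.1% to 4.3% | 0.1% |
| 0.9 | 6.9% to 7.4% | 3.5% to 3.7% | 0.0% |

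The first row agrees with the formulas within simulation error. The exact value for its last column is 2 × 0.025 × 0.5 = 2.5%.

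**After the change**

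With one deciding measure the error is 5% two-sided, or 2.5% for a false reduction. If both measures were kept as deciding and each tested at 0.025, the two-sided error would be 1 − 0.975² = 4.9%.

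**The case against.** **Only reductions count as success.** The endpoint asks for a reduction, so a significant worsening would not meet it. On that count the error is at most 4.9% and does not exceed 5%. This stands, and it is why both figures are given. It is still up to double the 2.5% that one measure would carry.

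**A contradictory result is improbable and would be seen.** Chance alone produces it in about 2.5% of studies or fewer, and section 12.2 also reports severity and area under the curve, so the pattern would be visible. That also stands. Visibility does not settle how such a result is classified, however: as written, it meets the endpoint.

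**This is a small, non-randomised pilot, and an analysis plan may exist.** Strict error control matters less here, and a multiplicity method may properly be left to such a plan. But the protocol itself fixes the 'or', the several primaries and the significance threshold. A later plan that chose one measure would depart from section 6.3, not complete it. Section 23 also expects the findings to feed a departmental review of how hypoglycaemia is managed.

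**A reader might infer that all eight primary items are tested at P<0.05.** That would give 1 − 0.95⁸ = 33.7% if independent and make a false success seem likely. The documents do not support this. The threshold is a general statement, and section 12.2 names a test only for frequency and time in range. The other items are agreement, detection or subgroup statements with no named test, and PPV and NPV have no null value. The 33.7% would describe tests that the protocol does not plan.

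**Conclusion.** The point holds for the unblinded endpoint of Arm 2 and, as a matter of labelling, for the unranked list of primary items. Following sections 6.3 and 12.2 as written, the chance of at least one P<0.05 under no effect is up to 9.75%, or about 7% to 9% at correlations of 0.9 to 0.5. The chance of a false reduction is up to 4.9%, against 2.5% for one measure. A fall in one measure counts as success even if the other worsens; this is possible under the rule but improbable by chance. A false success is therefore not shown to be likely.

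The figures assume two-sided tests that hold their nominal level; the ranges for dependent measures also rest on assumed correlations and normally distributed differences. They apply to the two named tests only. The change is worth making because it costs little, but the weakness does not undermine a feasibility study as such.

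**What to change.** - **Section 6.3, unblinded phase.** Replace the 'or' with one deciding measure, fixed before data are seen, and report the other as supporting. One candidate is CGM time in the hypoglycaemic range per 24 h of wear. The scaling is needed because the blinded phase lasts up to 10 days and the unblinded phase up to a further 20; at a constant daily rate, full use of both would double a raw total (20/10 = 2). Episode rate per 24 h would serve equally well for error control. The documents do not settle which measure matters more, so the choice is the investigators'.
- **Sections 6.1 and 6.3.** Name one primary endpoint per arm and relabel the rest as secondary or exploratory.
- **Section 12.2.** Confine the P<0.05 rule to a primary endpoint that has a stated null hypothesis. Report everything else with 95% confidence intervals and no significance claim, using exact intervals for PPV and NPV.

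This is rewording in three sections, with no extra patients, visits or data. The downside is that fewer endpoints can be called significant.
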